9.3 Secondary Outcome Measures

Secondary effectiveness and safety outcome measures will be assessed at the timepoints described below.

The secondary safety outcome measure at 24 and 36 months will include all device or procedure-related adverse device effects, SAEs and unanticipated adverse device effects (UADE) are defined in **Section 14 Adverse Event Reporting**.

Any medical surgical intervention to treat abnormal bleeding following the ablation procedure is considered a treatment failure. If menstrual status is assessed as "High/Heavy" by the investigator at the 24 or 36-month follow-up, the patient will be considered a treatment failure.

Secondary effectiveness outcome measures will include the following:

Patient Global Evaluation (PGE): at 6, 12, 24 and 36 months

- Patient satisfaction with treatment
- Menstrual status
- Recommend to friends

Investigator Global Evaluation (IGE): at 6, 12, 24 and 36 months

- Investigator satisfaction with treatment
- Menstrual status

Quality of Life Measures: at 6, 12, 24 and 36 months

- Improvement of quality of life as measured by:
 - Menorrhagia Impact Questionnaire (MIQ)
 - o Dysmenorrhea-related Numerical Rating Scale (NRS) pain score

Procedure:

•

- Endometrial ablation procedure-related Numerical Rating Scale (NRS) pain score
 - The following parameters will also be collected:
 - Total procedure time
 - Total treatment time (total energy delivery time)

Page 24 of 65

CONFIDENTIAL & PROPRIETARY

- Total procedure energy in joules
- Anesthesia regimen
- Procedure-related pain at pre-procedure (baseline), discharge and 24-hours postprocedure
- Need for cervical dilation

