11.3.1 Inclusion Criteria

Patients eligible for inclusion in this study must fulfill the following criteria:

- 1) Female patient age 30 to 50 years
- 2) Excessive menstrual bleeding due to benign causes
- 3) Uterine sounding depth measurement of 6.0 12.0cm (external os to internal fundus)
- 4) A minimum uterine cavity length of 4.0cm (internal os to internal fundus)
- 5) A minimum PBLAC score of ≥ 150 for 1 menstrual cycle (obtained during screening) and must also have a documented history of excessive menstrual bleeding prior to study enrollment
- 6) Endometrial biopsy within 12 months prior to treatment procedure with no abnormal pathology
- 7) Premenopausal at screening as determined by FSH measurement \leq 40 IU/L when age is \geq 40 years
- 8) Patient agrees to use a reliable form of contraception during the study, and follows these requirements:
 - a. If a hormonal birth control method is used for contraception, the patient must have been on said method for ≥ 3 months prior to the onset of the screening menstrual cycle and agrees to remain on the same hormonal regimen through the initial 12-month follow-up (pills, injections, patches, rings, implants)
 - b. Patient also agrees to not use hormonal birth control during the first 12-month posttreatment follow-up period if they were not using hormonal birth control during the 3 months prior to treatment
- 9) Ability to provide written informed consent
- 10) Patient is literate and clearly demonstrates understanding on how to use PBLAC after training
- 11) Patient agrees to the following during the study:
 - a. No initiation of hormonal contraception or any other medical intervention for bleeding
 - b. Attend all follow-up exams and submission of completed PBLAC diaries through the 36month follow-up timepoint

c. Exclusive use of study-provided sanitary products and submission of completed PBLAC diaries through the 12-month post-treatment follow-up

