12.9 Durability Visits Conducted 24 and 36 Months (± 8 weeks) After Treatment

The 24 and 36-month visit may be conducted via phone, letter, email or in person as described in Section 12.1.

The 36-month visit is the final study visit. Complete both the 36-Month Visit and the Study Completion eCRFs.

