13.2 Demographic Data and Medical History

Demographics are to be collected on all patients during screening, including age (based on day of consent), sex, race, and ethnicity. Height in centimeters (cm), body weight (kg, in indoor clothing but without shoes) and BMI will also be measured. BMI shall be calculated as kg/m2. The site should use the NIH website BMI calculator https://www.nhlbi.nih.gov/health/educational/lose_wt/BMI/bmi-m.htm. Alternatively, BMI can be calculated in EDC so long as height (cm) and weight (kg) are entered accordingly. Relevant specific medical history and current medical conditions will be captured.

Collect relevant medical diagnoses, specific medical history, surgical history and current medical conditions. In order to qualify, patients must have documented history or diagnosis of HMB, and therefore, source documents from non-participating institutions may need to be requested. History may also include failed or contraindication to medical therapy, subject-reported historical use of sanitary products consistent with HMB, menstrual cycles that interfere with normal daily activities (e.g., work, social/leisure) due to prolonged duration or heavy menstrual flow, date of subject's first perception of or when treatment was first sought for HMB, or assigned diagnosis code(s) consistent with HMB.

Other eligibility criteria potentially identified from medical history (not an inclusive list):

- Untreated/unevaluated cervical dysplasia, except cervical intraepithelial neoplasia I (CIN I)
- Previous endometrial ablation procedure
- Known/suspected abnormal uterine/pelvic anatomy or condition, such as frozen pelvis

Page 36 of 65

CONFIDENTIAL & PROPRIETARY

- Previous medical/surgical treatments, or has other conditions, that could lead to anatomic/pathologic weakness or thinning of the myometrium (Classical caesarean section and transmural myomectomy are examples of such treatments that may interrupt the integrity of the uterine wall)
- Known clotting defects or bleeding disorders
- Abdominal pelvic or gynecological malignancy

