13.8 Complete Blood Count (CBC) and Serum FSH

Complete Blood Count (CBC) and Serum Follicle Stimulating Hormone (FSH) test results may be obtained from the patient medical records if the test was performed 6 months or fewer from the procedure date.

Conduct additional testing as needed to confirm eligibility criteria.

Premenopausal status is to be confirmed by FSH measurement \leq 40 IU/L when the patient is \geq 40 years old.

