17.1.1 Intent-to-Treat (ITT) Cohort

All patients who are enrolled in the study (enrollment defined as patients who met all study eligibility criteria and in whom the procedure is initiated) are included in the Intent-to-Treat (ITT) cohort.

The ITT cohort will be used for the following analyses (as defined in Section 9.1 & 9.2):

- Primary safety and effectiveness analyses at 12-month follow-up visits.
- Safety & effectiveness analyses at 24, and 36-month follow-up visits.

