17.7 Subgroup Analyses

The following subgroup analyses will be performed for both treatment success (reduction of menstrual blood loss) and amenorrhea rates for the following timepoints during study follow-up: 12, 24, and 36-months post procedure.

- Age (<40 years vs. >40 years)
- Active bleeding at the time of the operative visit (Yes vs. No)

- Transverse or low segment C-section (Yes vs. No)
- Anesthesia regimen (None vs. Sedation vs. Local Anesthesia vs. General Anesthesia vs. Multiple)
- Use environment (Office vs. Non-office)
- Uterine sound depth (6-9.0cm vs. 9.1-12cm and 6-8.0cm vs. 8.1-10cm vs. 10.1-12cm)
- Presence of anemia at Baseline defined as hemoglobin < 12 g/dL (Yes vs. No)
- Presence of fibroids at Baseline (Yes vs. No)
- Presence of ovarian cysts at Baseline (Yes vs. No)
- Presence of any intrauterine pathology at baseline (Yes vs. No)
- Contraceptive use (hormonal method vs. non-hormonal method)
- COVID-19 Status (diagnosed with COVID-19 vs. did not have COVID-19)
- COVID-19 Vaccination Status (vaccinated vs. not vaccinated)

The study is not powered for these subgroups, and therefore, there will be no hypothesis testing for the primary endpoints within these groups. These analyses will be done using the PP population.

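### Late amenorrhea rates are biased upward, increasingly with follow-up, because menopausal status is checked only at screening and nothing separates natural menopause from device effect

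*Combined protocol and SAP*

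**What the plan says.** - **Entry.** Section 11.3.1 admits "Female patient age 30 to 50 years", and Section 13.2 fixes age on the day of consent. The same list requires women to be "Premenopausal at screening as determined by FSH measurement" of at most 40 IU/L, applied only from age 40.
- **Timing of the check.** Table 12-1 lets the FSH result be 180 days old at treatment. Table 23-1 marks FSH in the screening column and nowhere else.
- **Late visits.** Section 12.9 is headed "Durability Visits Conducted 24 and 36 Months". Section 17.1.1 lists "Safety & effectiveness analyses at 24, and 36-month follow-up visits" for the ITT cohort. Section 17.7 reports success and "amenorrhea rates for the following timepoints during study follow-up: 12, 24, and 36-months post procedure" by subgroup in the PP cohort.
- **How late bleeding is measured.** Section 13.11.2 and Table 23-1 end diary collection at month 12. Status at months 24 and 36 therefore comes from the patient and investigator global evaluations (Attachment D), whose no-bleeding box records no cause.
- **Late failure.** Under Section 9.3, any intervention for abnormal bleeding after the ablation is a failure. So is a menstrual status rated high or heavy "by the investigator at the 24 or 36-month follow-up, the patient will be considered a treatment failure".
- **Other causes of amenorrhea.** Section 13.9 and the footnotes to Table 23-1 consider pregnancy. Nothing considers menopause. The only age split is under 40 against over 40.

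**The concern.** At months 24 and 36 the outcome is the presence or heaviness of bleeding. A woman who has reached menopause ticks no bleeding and cannot be rated heavy. If she has had no intervention, she counts as amenorrheic and as a success, and nothing on the form shows whether the ablation or her age is the reason.

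A randomised control arm would age alongside and show the background rate. This study has one arm, and its 66% benchmark applies to one-year success only. Nothing therefore shows how much late amenorrhea would have occurred anyway. The error always favours the device and grows with each year. At stake is how the 24- and 36-month figures are read: a fading effect can be masked, or ageing can be taken for continuing benefit.

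**Working it through.** **The plan's own figure.** The plan states no menopause or late-rate figure. Its sample size, which concerns the 12-month endpoint only, reproduces: [(1.96√(0.66×0.34) + 0.842√(0.78×0.22)) / 0.12]² = 113.26, so 114. Adding 10% gives 125.4, so 126.

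**Age at the last visit.** Consent at exactly 50 plus 36 months of 30 days gives 50 + 1080/365.25 = 52.96. Consent just before 51, treatment 180 days later and a visit at the end of the 8-week window gives 50.999 + (180 + 1080 + 56)/365.25 = 54.60.

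**Share m reaching the last period after treatment (assumptions).** Entry age is normal with mean 40, 42 or 44 and SD 5, truncated to 30 up to the 51st birthday. Age at last period is normal with (mean, SD) of (50, 4), (51, 4), (52, 4) or (51, 5). For a woman of age x, the probability within h years is 1 − S(x+h)/S(x), averaged over entry age.

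| Group | m by month 36 |
|---|---|
| Mean entry age 40 | 5-10% |
| Mean entry age 42 | 8-14% |
| Mean entry age 44 | 12-19% |
| Entered under 40 | 0.2-1.8% |
| Entered at 40 or over | 10-25% |
| Entered under 45 | 2-8% |
| Entered at 45 or over | 24-39% |

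At mean entry age 42, m grows from 2-4% at month 12 to 5-9% at month 24 and 8-14% at month 36.

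**From share to bias.** The share is not the bias. Assume menopause is independent of the device result. With true device amenorrhea a, the observed rate is a + m(1 − a), so the inflation is m(1 − a). With a proportion u who would otherwise be heavy and untreated, and no interventions, success is inflated by m × u.

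- Amenorrhea, a = 50%: 0.5 × 5.4% = 2.7 points to 0.5 × 19.4% = 9.7 points.
- Success, u = 10%: 0.1 × 5.4% = 0.5 points to 0.1 × 19.4% = 1.9 points.

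**Coarser check.** Let a share w = 10-30% of the cohort be at risk, with annual hazard h = 5-20%, so m(t) = w(1 − (1 − h)^t). At three years, 0.1(1 − 0.95³) = 1.4% and 0.3(1 − 0.8³) = 14.6%. The inflation is 0.7 to 7.3 points for amenorrhea and 0.1 to 1.5 points for success.

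**Must the observed rate rise?** Let I be cumulative interventions, so observed success is (1 − I)(1 − u(1 − m)). The runs below take u = 10% and the largest share of the coarser model (w = 30%, h = 20%).

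| Scenario | Month 12 | Month 24 | Month 36 |
|---|---|---|---|
| Success, no interventions | 90.6% | 91.1% | 91.5% |
| Success, 1% interventions a year | 89.7% | 89.3% | 88.7% |
| Amenorrhea, true rate 50/48/46% | 53.0% | 53.6% | 53.9% |
| Amenorrhea, true rate 50/46/42% | 53.0% | 51.8% | 50.5% |

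The direction depends on interventions and returning bleeding. The third row shows the hazard: the true rate falls by 4 points while the reported rate rises.

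**Month 12.** In the coarser model m is at most 0.3 × 0.2 = 6.0%. Even if every failure implied by the planning rate (22%) were untreated, success would gain at most 6.0% × 22% = 1.3 points.

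**The case against.** A reader might infer that late rates must rise with follow-up, or that every menopausal woman becomes a success whether or not the ablation worked. The documents support neither. Under Section 9.3 a woman who was treated for bleeding stays a failure, that component of success can only fall, and bleeding can return in others. Only the upward bias is built in.

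The other side has further points:

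- **Nothing decision-bearing is touched.** Section 17.6 tests no secondary hypothesis, Section 17.7 is descriptive and unpowered, and no trend test is planned. This stands.
- **Month 12.** The benchmark is itself a one-year rate, and the FDA letter quoted in Section 6 reports comparable populations and no significant effect of age above or below 40. This stands for the primary endpoint. It says nothing about months 24 and 36.
- **Existing cover.** Section 17.2 stratifies by baseline characteristics, Section 17.3 names demographics at 24 and 36 months, and Section 17.8 allows further exploration. The cover is partial: 17.2 concerns month 12, the 17.3 outcome is a diary score no longer collected after month 12, and 17.8 commits to nothing specific. The under-40 stratum is nearly free of the problem, but the older one mixes low and high risk.
- **The model may overstate.** Entrants have a recent score of at least 150 and, from age 40, FSH of at most 40 IU/L, which may lower near-term menopause. This is fair, and a reason to show the milder range.
- **Excluding menopausal women** conditions on a post-treatment event, and ablation amenorrhea can mask menopause. This stands, so exclusion belongs in a sensitivity analysis only. Resting durability on younger women alone would set aside part of the indicated population.

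**Conclusion.** The concern holds as an upward bias that accumulates in the late amenorrhea rate. The gap can be verified: one FSH check at screening, follow-up to age 53-54, bleeding boxes without cause, and no handling of menopause anywhere.

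The size rests on assumptions outside the documents: the age mix, the last-period ages, a 50% true amenorrhea rate, 10% heavy and untreated, and independence. On those, the inflation at month 36 is about 3-10 points for amenorrhea (0.7-7 in the coarser model) and about 0.1-2 points for success. Amenorrhea is the outcome to protect; the effect on freedom from heavy bleeding is small. The primary test and sample size do not depend on this. It limits what the 24- and 36-month figures can say about durability, and is worth correcting because the correction is cheap.

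**What to change.** 1. **Section 17.7.** Report 24- and 36-month amenorrhea, and success, descriptively by age at entry under 45 against 45 or over, in addition to the split at 40. As printed, a woman aged exactly 40 falls in neither group; assign her to one.
2. **eCRF and Table 23-1.** Add one item at months 24 and 36, answered from the existing contact and medication review: menopause diagnosed by a clinician or menopausal hormone therapy started (yes/no, date). No blood test or extra visit is needed.
3. **Sensitivity analysis.** Beside the all-ages rate, repeat the late amenorrhea rate without those women, and state that ascertainment is incomplete because ablation amenorrhea can mask menopause.
4. **Reporting.** Any durability statement should show the all-ages and age-stratified rates together.
5. **Reconcile the diary period.** Inclusion criterion 11b in Section 11.3.1 has diaries submitted through month 36, while 11c, Section 13.11.2 and Table 23-1 stop at month 12. This decides how late amenorrhea is measured.

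The cost is analysis-plan wording, one eCRF field and a few tables with small denominators. Under the entry-age assumptions above, about 15-37% enter at 45 or over. Of 114 evaluable women that is 17 to 42, giving a 95% half-width at a 50% rate of 1.96√(0.25/17) = 24 points to 1.96√(0.25/42) = 15 points. The 12-month primary analysis is unchanged.

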17.8 Exploratory Analyses

The following exploratory analyses will be performed:

- Mean percent change in PBLAC score from Baseline per PGE Patient Satisfaction Category Question 1 (Very Satisfied, Satisfied, Not Sure, Dissatisfied, Very Dissatisfied)
- Average change in quantity of sanitary products used
- Relation between Baseline PBLAC score and treatment success or failure
- Change in pain medication use for dysmenorrhea from baseline to 12 months

Additional exploratory analyses may be performed.

18 STUDY RECORD MANAGEMENT

For the study duration the investigator will maintain complete and accurate documentation, including but not limited to, medical records, study progress records, source worksheets, laboratory reports, eCRFs, signed and dated informed consent forms, all relevant correspondence (e.g., with the IRB, Sponsor personnel/representatives, and other regulatory agencies), the protocol, and documentation for each deviation from the protocol, records of receipt, use, or disposition of each device, record of the exposure to the investigational device, adverse event records, information regarding patient discontinuation or completion of the study, any other supporting data, and any other records that FDA requires to be maintained by regulation or by specific requirement.

18.1 Source Documentation

Regulations require that an investigator maintain information in the patient's medical records which can corroborate data collected on study eCRFs. In order to comply with these regulatory requirements, at a minimum, the following information should be recorded in the patient's study records:

- Medical history and physical condition of the patient prior to participation in the study sufficient to verify inclusion/exclusion criteria.
- Dated and signed study progress or clinic notes on the day of entry into the study referencing the protocol number, site, unique patient ID number assigned, and a statement that informed consent was obtained.
- Dated and signed notes from each patient's visit.
- All collected AE, SAE, UADEs and their resolution, including supporting documents such as discharge summaries and diagnostic test results.
- Patient medical condition upon completion of or withdrawal from the study.

Data recorded in the patient's medical records will be reviewed for verification of agreement with critical data on the eCRFs as specified in the monitoring plan. The investigator/study personnel will allow the Sponsor (or designee) and appropriate regulatory authorities access to these records. If a non-study physician, at a non-study institution, sees a study patient regarding a study requirement or an AE, SAE or UADE, then a copy of the medical record will be copied and placed in the patient's study records and made available for review.

18.2 Data Collection and Electronic Case Report Form Completion

All study data will be collected and recorded by authorized study personnel on the required electronic Case Report Forms (eCRFs). Identifiable patient information will not be recorded in the eCRFs. Patients will be assigned unique study identification numbers. Only study site personnel directly involved with study and Sponsor, monitors or designee(s) will have access to the documentation that links the study identification numbers to identifying patient information.

The eCRFs will capture information relevant to the patients' clinical presentation, medical history, laboratory values, and results of clinical and/or gynecological testing. Follow-up clinical data will include laboratory assessments, current medications, physician office visits, hospitalizations, and/or adverse events that have occurred since study enrollment or from the prior visit.

The site PI will be required to sign and date the completed eCRFs on the appropriate page(s) to verify that he/she has reviewed the recorded data, and assures its accuracy and completeness.

18.3 Investigational Devices

18.3.1 Labeling

The Sponsor will label all investigational devices in accordance with FDA regulations per 21CFR 812.5.

18.3.2 Ordering, Receiving and Storing Investigational Device

The Sponsor will ship Investigational devices to a clinical site once the requirements for site activation and authorization to enroll are met.

Components of the investigational device system will be shipped to each investigational site with a packing slip. The packing slips will be verified to ensure that they reflect the correct shipping quantities and will be signed and dated by the study personnel upon receipt of the devices. A copy of the signed packing slip should be provided to the Sponsor or designee.

Investigational devices shall be stored in a secure area. The PI or an authorized designee will be responsible for maintaining control of and verifying each device's disposition.

Page 50 of 65

CONFIDENTIAL & PROPRIETARY

18.3.3 Investigational Device Accountability

The Investigator shall maintain adequate records of the receipt, use, and disposition of the Investigational Device.

Investigational devices will only be used with this clinical investigation. The principal investigator or an authorized designee shall keep device accountability log tracking documenting the receipt, use, return and disposal of the investigational devices, which shall include:

- a) the date of receipt and the signature of the individual who received the product(s),
- b) identification of each investigational device (batch number/serial number or unique code),
- c) the expiry date, if applicable,
- d) the date or dates of use,
- e) unique patient identification number,
- f) date when the investigational device was returned (for any reason), and
- g) the date of return of unused, expired or malfunctioning investigational devices, if applicable.

This log must be maintained at each investigational site and must be filed in the regulatory binder. At the end of enrollment, Sponsor or designee shall ensure that documentation of the final reconciliation of all devices is signed or initialed by the PI or authorized designee.

18.3.4 Device Disposal or Return

Devices are to be disposed utilizing the study site's specific biohazard procedures unless return is required or requested by the Sponsor.

Devices that did not work as expected (device deficiency or malfunction) or are involved with an adverse event during treatment may be returned. If a Sponsor representative is present, work with them to complete the device return. If not, then, please contact the Sponsor clinical staff as soon as possible to discuss the return of products. The Sponsor will provide instructions for biohazard device return. Return of these devices will be captured on the device accountability log.

A Sponsor representative or designee will collect all unused devices remaining at the end of the enrollment period.

